COMIRB Protocol

COLORADO MULTIPLE INSTITUTIONAL REVIEW BOARD
[name] [contact] [contact]

Protocol #: 16-1785

Project Title: Evaluation of Moderate to Severe Influenza Disease in Children 6 months to 8 years in Colorado

Principal Investigator: [name]

Version Date: 7/27/16

I. Hypotheses and Specific Aims:

Children 6 months to 8 years of age with moderate to severe influenza have a higher risk of hospitalization, intensive care unit (ICU) admission, antibiotic use and complications compared with children with mild influenza illness.

Specific Aims:

Aim #1: To determine the validity of the moderate to severe endpoint for influenza as a predictor for hospitalization among children aged 6 months to 8 years evaluated at Children's Hospital Colorado (CHCO) emergency department (ED) and urgent cares (UC) during the 2016-2017 influenza season.

Aim #2: To prospectively evaluate the usefulness of the moderate to severe influenza endpoint against additional severity measures such as ICU admission, antibiotic and antiviral use, parental and child absenteeism and recurrent healthcare visits among children aged 6 months to 8 years evaluated at ED and UC centers in Colorado.

Aim # 3: To compare the healthcare costs associated with management of moderate to severe versus mild influenza disease.

Exploratory Objectives:

- 1) To compare the moderate to severe influenza definition, and other severity measures such as ICU admission, hospitalization, antibiotic, antiviral use, child and caregiver absenteeism among patients vaccinated with injectable influenza vaccine (IIV) versus unvaccinated individuals.
- 2) To evaluate severity measures such as hospitalization, ICU admission, antibiotic, antiviral use, caregiver and child absenteeism among children with influenza like illness who test negative for influenza.
- 3) To determine whether clinical measurements taken at ED/UC presentation such as systemic inflammatory response syndrome (SIRS) criteria, adjusted heart rate, oxygen saturation and temperature predict hospitalization, ICU admission and having polymerase chain reaction (PCR)-confirmed influenza. We will also consider the prediction value of peak temperature and temperature duration.

II. Background and Significance:

Influenza is an important cause of morbidity in children, annually causing 1-7 hospitalizations per 10,000 in US children under the age of 18 years (1-6). Children are

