The purpose of the proposed study is to validate that the definition of moderate to severe influenza in children predicts greater risk of healthcare endpoints such as hospitalization, increased length of stay, use of antimicrobials (including antivirals), absenteeism, increased duration of illness, and increased healthcare costs.

Understanding and validating the relationship between moderate to severe influenza and these clinically relevant endpoints is critical to establishing relevant surrogate markers of clinical and public health outcomes. If shown to be clinically relevant, this definition of moderate to severe influenza can be an important endpoint for assessing influenza vaccine effectiveness.

III. Preliminary Studies/Progress Report:

CHCO provides an ideal site for the study of influenza in children. CHCO is a large tertiary institution with a large catchment area of Denver Metro, Aurora and surrounding states. It serves 67% of children in the state of Colorado. From December 1, 2010 to April 30, 2014, there were 409 patients admitted to CHCO with PCR-confirmed influenza; 62% of these were defined as high-risk (16), and 38% were vaccinated against influenza during the same season. Accurate immunization data was available for 83% of patients via the Colorado Immunization Information System (CIIS). Clinical presentation and

hospital-based outcomes such as length of hospitalization among children admitted with influenza are shown in Table 1.

Table 1. Children Admitted To CHCO with Influenza, 2010-2014

Children admitted to CHCO with influenza N = 395	< 3 years N = 156	>3 years N = 239
Otitis media	10 (6)	6 (3)
Pneumonia	7 (5)	22 (9)
Hypoxia	19 (12)	141 (59)
Fever	133 (85)	207 (87)
Median duration of fever, days (range)	2 (1-17)	4 (1-64)
Tachypnea	64 (41)	91 (38)
Antibiotics	88 (56)	157 (66)
Median duration of antibiotics, days (range)	7 (0-23)	8 (0-77)
Pediatric Intensive Care Unit (PICU)	55 (35)	81 (34)
PICU length of stay, days	2 (1-100)	3(1-83)
Death	1 (1)	2 (1)
Median duration of hospitalization, days (range)	3 (1-100)	3 (1-128)
Vaccinated during current season against influenza	39 (25)	87 (36)

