Preliminary data from the 2013-2014 and 2014-2015 influenza seasons demonstrated that among 11,997 patients who presented to CHCO ED, UC or outpatient clinics for an acute respiratory illness, 1398 (12%) underwent viral testing (either respiratory pathogen panel multiplex PCR or influenza PCR). 1375 patients were admitted for a respiratory illness, and of these, 994 (72%) underwent viral testing. Additional data regarding ED visits during these time periods are shown in Table 2.

Table 2. Children Presenting to CHCO ED or UC with Acute Respiratory Illness, 2013-2014 and 2014-2015

CHCO data:	2013-2014	2014-2015	Total
ED/UC/Clinic visits due to an acute respiratory illness	5900	6097	11997
ED visits due to an acute respiratory illness, limited to patients < 8 yrs	4510	4595	9105
ED visits limited to CHCO, Uptown Urgent Care, South Urgent Care with an acute respiratory illness, limited to patients < 8 yrs	2703	2809	5512
ED visits with above restrictions further limited to Jan to March	1290	1745	3035
Limit visits to < 8 yrs Jan to March, no repeat visits	1244	1688	2932
Admission for acute respiratory illness,	454	486	940

Jan -Mar

IV. Research Methods

The study comprises a prospective analysis of children presenting to CHCO ED, and North Campus UC with an influenza-like illness (ILI) during the 2016-2017 influenza season. Once enrolled in the study, we will collect respiratory samples (nasopharyngeal (NP) specimens), socio demographic, and clinical data including variables of interest outlined above, and follow the clinical outcome of these children for 14 days after their initial presentation. A complete list of the variables being collected can be found in Appendix A.

A. Outcome Measure(s):

Primary outcome measure /Endpoints:

- 1) Hospitalization in patients presenting to the CHCO Main ED or North Campus UC with influenza

Secondary outcome measures/Endpoints:

- 1) ICU admission in patients presenting to the CHCO Main ED or North Campus UC with influenza
- 2) Antiviral use in patients presenting to the CHCO Main ED or North Campus UC with influenza
- 3) Antibiotic use in patients presenting to the CHCO Main ED or North Campus UC with influenza
- 4) Number of visits to the ED or healthcare provider in patients presenting to the CHCO Main ED or North Campus UC with influenza
- 5) Number of days of absenteeism from school or daycare in patients presenting to the CHCO Main ED or North Campus UC with influenza

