- 2) Prior enrollment in study
- 3) Nurse only visit

C. Study Design and Research Methods

[figure not shown]
This will be a prospective observational cohort study conducted at the CHCO Main ED and North Campus UC.

Surveillance Methods:

The study group will review the CHCO Main ED or North Campus UC visits for patients meeting study criteria presenting with ILI. Screening will be conducted by designated professional research assistants (PRAs) at each site. The study team has a treatment relationship with potential subjects, since one of the co-investigators is an ED physician, thus enabling screening of potential patients. The parents/legal guardians of eligible patients will be approached for consent to obtain respiratory specimens for PCR testing, interviewed to obtain medical information pertaining to the current and future ILI visits, asked permission to obtain additional information (vaccination status, influenza vaccination type [LAIV] or IIV) and medical comorbidities) from the primary care provider, and to bank residual blood and respiratory samples. A memory aid card will be provided to the family member upon discharge from the ED/UC setting as an aide memoire, and the medical chart will be reviewed for additional clinical and demographic information. On day 14(+/-3) following the initial visit, caregivers of all participants who test positive for influenza will be contacted by phone to provide additional follow-up information regarding child and parental absenteeism, additional healthcare visits, duration of illness. Additionally, a random sample of participants whose influenza test is negative in a 1 to 4 ratio will be contacted for follow-up. A second chart review will occur at this time for details regarding additional visits or admissions. Data will be managed with REDCap (Research Electronic Data Capture) tools hosted at the University of Colorado (19) and exported to SAS 9.3 (Cary, NC) for statistical analyses.

A flow diagram summarizing the study methods is shown in Figure 1.

Figure 1. Flow diagram summarizing methods for proposed surveillance study

Specimen Testing:

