For all study objectives, we will present data descriptively using frequencies for categorical variables and measures of central tendency for continuous variables. We will explore bivariable associations between moderate to severe versus mild influenza for covariates including demographic factors and clinical factors outlined above. Proportions will be compared using Chi-square test. Mean values will be compared using student's t test for normally-distributed data, otherwise Wilcoxon-Rank-Sum test will be used.

Aim #1/Primary Endpoint Analysis: We will use logistic regression to estimate odds ratios (and 95%CI) for hospitalization, adjusted for significant covariates at the level of $P < 0.2$ on bivariable analysis; and other covariates selected *a priori* that could affect outcomes such as hospitalization (age group, high risk medical condition, vaccination status, influenza type). We will verify to ensure statistical assumptions are met for each model. The intraclass correlation coefficient will be estimated and a multi-level model will be used if we need to account for multiple visits per child. If we use a multi-level model, the optimal covariance structure will be determined through the examination of information criteria statistics and graphical techniques.

Aim #2/Secondary Endpoint #1-6 Analysis: We will use logistic regression to estimate each of our dichotomous secondary outcomes of interest, ICU admission, antibiotic,

antiviral use, adjusted for significant covariates at the level of $P < 0.2$ on bivariable analysis; and other covariates selected *a priori* that could affect outcomes such as hospitalization (age group, high risk medical condition, vaccination status, influenza type). We will verify to ensure statistical assumptions are met for each model. The intraclass correlation coefficient will be estimated and a multi-level model will be used if we need to account for multiple visits per child. If we use a multi-level model, the optimal covariance structure will be determined through the examination of information criteria and graphical techniques. We will also explore our secondary outcomes of interest expressed as continuous variables (number of recurrent visits to the ED, duration of absenteeism in days). We will use a log linear model to compare these variables between the mild versus moderate to severe influenza groups and will exponentiate the coefficients to yield geometric mean ratios.

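### The return-visit analysis names only ED visits although secondary endpoint 4 covers any healthcare provider, and it makes no allowance for days spent in hospital

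*Combined protocol and SAP*

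**What the plan says.** Four places describe the return-visit outcome.

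- Section I, Aim #2 lists "parental and child absenteeism and recurrent healthcare visits" among the severity measures.
- Section IV.A, secondary endpoint 4, is "Number of visits to the ED or healthcare provider in patients presenting to the CHCO Main ED or North Campus UC with influenza".
- Section IV.C, Surveillance Methods: the day-14 (±3) caregiver call asks about "child and parental absenteeism, additional healthcare visits, duration of illness", and a second chart review looks for further visits and admissions.
- Section IV.F, Aim #2 analysis, gives the continuous secondary outcomes as "number of recurrent visits to the ED, duration of absenteeism in days" and continues: "We will use a log linear model to compare these variables between the mild versus moderate to severe influenza groups". Coefficients are exponentiated to geometric mean ratios.

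On timing, the opening paragraph of Section IV says the study will "follow the clinical outcome of these children for 14 days after their initial presentation". The window therefore starts at presentation, not at discharge. No section says how a child admitted at the index visit enters the count, whether a readmission is a visit, or that inpatient days leave the time at risk. The multi-level model in Section IV.F is there for several visits per child; it does not address time at risk.

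**The concern.** Two separate problems affect one secondary endpoint.

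First, the analysed variable is narrower than the endpoint. Taken literally, Section IV.F leaves out returns to primary care and other providers, although the study asks for them at follow-up. If this is not settled beforehand, the analyst has to choose between two definitions with the data in hand.

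Second, a child cannot make an outpatient return while an inpatient. Aim #2 treats more return visits as a sign of more severe illness, and the study's hypothesis is that moderate-to-severe cases are admitted more often. That group would then have less time in which to return, and its count is lowered by the very event the primary analysis expects to find. A ratio near 1 could be read as the definition failing to predict repeat healthcare use when part of the explanation is lost time at risk.

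**Working it through.** **Definition.** Set side by side, Aim #2 (healthcare visits), endpoint 4 (ED or healthcare provider) and the day-14 call (additional healthcare visits) agree with each other. Section IV.F (ED) does not. The direction of the effect is open: ED-only counting misses clinic visits after discharge in admitted children, and also misses provider visits in mild cases.

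**Time at risk.** The plan states no expected value for return visits, so there is no figure of its own to reproduce here.

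Inputs from the documents:
- Window: 14 days from presentation (Section IV).
- Length of stay L: median 3 days in both age groups, ranges 1–100 and 1–128 (Table 1). The mean is not given.
- Admission odds ratio: 2, or 3 for the smaller sample (Section IV.F, power).
- Group sizes: 30% and 70% of 408, that is about 122 mild and 286 moderate-to-severe.

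Assumed: the admission rate in mild influenza, p0, which is not stated; the range used is 10% to 32%. The top is 940/2932 = 32.1% from Table 2, a rough ratio because the two rows carry different restrictions and cover all acute respiratory illness. The middle value, 20%, is close to what the stated sample sizes imply: a two-proportion calculation at 20% gives 420 for an odds ratio of 2 and 157 for an odds ratio of 3, against the stated 408 and 151.

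The moderate-to-severe admission rate follows from p1 = OR × odds0 / (1 + OR × odds0), with odds0 = p0/(1 − p0). If daily return rates out of hospital are equal in the two groups, the ratio of mean counts that would be observed is

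(1 − p1 × L/14) / (1 − p0 × L/14).

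Example with p0 = 0.20, OR = 2 and L = 3: p1 = 0.333; numerator 1 − 0.0714 = 0.929; denominator 1 − 0.0429 = 0.957; ratio 0.97.

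| p0 | OR | p1 | Mean stay 3 days | Mean stay 7 days | Admitted child never returns |
|---|---|---|---|---|---|
| 0.10 | 2 | 0.182 | 0.98 | 0.96 | 0.91 |
| 0.20 | 2 | 0.333 | 0.97 | 0.93 | 0.83 |
| 0.32 | 2 | 0.485 | 0.96 | 0.90 | 0.76 |
| 0.10 | 3 | 0.250 | 0.97 | 0.92 | 0.83 |
| 0.20 | 3 | 0.429 | 0.95 | 0.87 | 0.71 |
| 0.32 | 3 | 0.585 | 0.94 | 0.84 | 0.61 |

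Only the 3-day column rests on a stay length from the documents, and it takes the median as the mean. The 7-day column is an assumption. The last column, (1 − p1)/(1 − p0), is a bounding case and not an expectation.

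**Scale against sampling error.** At an assumed mean of 0.3 returns per child, the standard error of the log ratio is √(1/(0.3 × 122) + 1/(0.3 × 286)) = √(1/36.6 + 1/85.8) ≈ 0.20. The 95% interval then runs from the estimate divided by about 1.47 to the estimate times about 1.47. A shift of 2–6% lies well inside that.

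**With the correction.** Dividing each group's count by its days out of hospital returns the ratio to 1.00 when the daily return rates are equal.

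**The case against.** The strongest reply is that the ED wording is shorthand. The Section IV.F paragraph is headed as covering secondary endpoints 1–6, so endpoint 4 as defined falls under it. Table 2 also uses ED visits loosely, with a row that counts two urgent-care sites under that label. This stands in part: it cannot be said that urgent-care returns are definitely dropped. It does not rescue returns to other providers, which no reading of ED includes.

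On time at risk, a reader might infer that the plan scores a child admitted at the index visit as having few or no returns, so that the sickest children come out best. The documents contain no such rule; they are silent. With a 3-day stay, an admitted child still has about 11 of 14 days in which to return. A reader might also infer that moderate-to-severe influenza will appear to lead to fewer returns than mild. That needs a true ratio close to 1, or an effect well above the 2–6%, and the documents give no return-visit rates from which to argue it.

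Two further points stand. The working uses ratios of arithmetic means, whereas the plan reports geometric mean ratios, so the table shows direction and order of size and not the exact bias in the planned estimate. And hospitalization is the primary outcome and also enters the cost comparison, so a low return-visit ratio would not be read alone.

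The obvious remedy, comparing only children sent home from the index visit, has its own flaw. It conditions on index admission, which is essentially the primary outcome; moderate-to-severe children sent home are likely to be the less ill of their group.

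**Conclusion.** The mismatch between endpoint 4 and its analysis is definite and should be corrected; its effect on the result has no determinable direction. The lack of allowance for inpatient time is also definite, and the direction follows from the study's own hypothesis: towards or below 1. Its size is modest, about 2–6%, given a mean stay equal to the 3-day median, mild admission of 10–32%, an admission odds ratio of 2 or 3, and equal daily return rates out of hospital. The long upper ranges in Table 1 allow a mean stay above 3 days, so a larger effect is possible, as it is if admission replaces later returns. The documents quantify neither. They do not support a claim that the endpoint will reverse or that it rewards severity. This is a clarification worth making to a secondary endpoint, and it does not threaten the primary analysis.

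**What to change.** In Section IV.F, Aim #2 analysis:

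1. Replace the ED-only variable with endpoint 4 as defined: return visits to any ED, urgent care or healthcare provider after the index visit or, for a child admitted then, after the index admission.
2. State whether and how a readmission counts.
3. Compare all influenza-positive children with a count model that uses days out of hospital during follow-up as exposure time, up to each child's actual follow-up date since the call may fall at day 14 ± 3. Children in hospital throughout have no time at risk; report their number. A count model also accommodates zero visits, which have no logarithm if the planned model transforms the outcome.
4. Present any comparison among children discharged home from the index visit as supplementary, with the note that it conditions on admission.

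The cost is slightly more analysis work. Admission and discharge dates must be taken from the planned second chart review, so confirm that the data form records them.

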- 6) Number of days of absenteeism from work in caregivers of children presenting to the CHCO Main ED or North Campus UC with influenza
- 7) Healthcare costs associated with ED visits or hospitalization in patients presenting to the CHCO Main ED or North Campus UC with influenza

Exploratory Outcome measures/Endpoints:

1) Vaccination status in subjects testing positive for influenza:

- a. Injectable influenza vaccine (IIV) receipt in patients presenting to the CHCO Main ED or North Campus UC with moderate to severe influenza
- b. IIV receipt in patients presenting to the CHCO Main ED or North Campus UC who are hospitalized
- c. IIV receipt in patients presenting to the CHCO Main ED or North Campus UC who are admitted to the ICU
- d. Number of days of fever in patients who received IIV presenting to the CHCO Main ED or North Campus UC
- e. Number of days of caregiver and child absenteeism in patients who received IIV presenting to the CHCO Main ED or North Campus UC

- f. IIV receipt in patients presenting to the CHCO Main ED or North Campus UC who received antibiotics
- g. IIV receipt in patients presenting to the CHCO Main ED or North Campus UC who received antivirals

2) Influenza-like-illness among subjects testing negative for influenza:

- a. Hospitalization in patients with ILI who test negative for influenza
- b. ICU admission in patients with ILI who test negative for influenza
- c. Duration of fever in patients with ILI who test negative for influenza
- d. Number of days of absenteeism from work in caregivers of patients with ILI who test negative for influenza
- e. Number of days of absenteeism from school in patients with ILI who test negative for influenza
- f. Antibiotic use in patients with ILI who test negative for influenza
- g. Antiviral use in patients with ILI who test negative for influenza

3) Fever, vital sign data and extrapulmonary complications:

- a. Number of days of fever in patients presenting to the CHCO Main ED or North Campus UC with influenza
- b. Peak temperature at any time during illness in patients presenting to the CHCO Main ED or North Campus UC with influenza
- c. Modified SIRS criteria met in patients presenting to the CHCO Main ED or North Campus UC with influenza
- d. Initial and peak adjusted heart rate in patients presenting to the CHCO Main ED or North Campus UC with influenza
- e. Oxygen saturation in patients presenting to the CHCO Main ED or North Campus UC with influenza

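### Recurrent visits and absenteeism days (secondary endpoints 4–6) can be zero, yet are to be reported as geometric mean ratios with no rule for zeros

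*Combined protocol and SAP*

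**What the plan says.** Section IV.A lists three secondary endpoints that are counts or days:

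- Endpoint 4: "Number of visits to the ED or healthcare provider in patients presenting".
- Endpoint 5: "Number of days of absenteeism from school or daycare".
- Endpoint 6: "Number of days of absenteeism from work in caregivers of children presenting".

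The Aim #2 analysis in Section IV.F handles them as continuous variables, described as "number of recurrent visits to the ED, duration of absenteeism in days". It compares mild with moderate to severe influenza by a log linear model and "will exponentiate the coefficients to yield geometric mean ratios". The text on Exploratory Objectives #1-2 reuses that model for absenteeism days. The only general safeguard, placed with the logistic models, is: "We will verify to ensure statistical assumptions are met for each model".

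Three other places bear on the point.

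- Section IV says the study will "follow the clinical outcome of these children for 14 days after their initial presentation". Section IV.C sets the follow-up call at day 14, plus or minus 3 days, with a second chart review at that time.
- Aim #2 in Section I speaks of "recurrent healthcare visits among children aged 6 months to 8 years", which is wider than the ED.
- The second sensitivity analysis in Section IV.F covers every secondary outcome. It proceeds to the temperature-only definition when the first comparison is significant with an odds ratio above 1.

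**The concern.** A geometric mean needs strictly positive values. A child with no return visit, a child who misses no school and a caregiver who misses no work all score zero. The plan gives no added constant, two-part model, count distribution or exclusion rule for them. By contrast, the cost analysis under Aim #3 names a generalized linear model as an alternative.

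The size of the reported ratio for endpoints 4–6 therefore rests on a choice that can be made after the data are seen. Aim #2 exists to judge the severity definition against outcomes such as these, so the size of the ratios is a main result of that aim.

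Four linked gaps affect the same endpoints:

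- Endpoint 4 includes healthcare-provider visits in Section IV.A but only ED visits in Section IV.F.
- Nothing says how the 14-day follow-up is applied when the call falls on another day.
- Nothing separates zero days absent from not applicable. Enrolment starts at 6 months of age, and some children will not attend daycare and some caregivers will not work.
- The sensitivity-analysis gate asks for an odds ratio that these endpoints do not produce.

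**Working it through.** **1. Two readings of the model.** If log(y) is regressed, the exponentiated coefficient is a geometric mean ratio, but log(0) does not exist. If a count model with log link is fitted, zeros are accepted, but the exponentiated coefficient is a ratio of arithmetic means. The name of the model does not settle which is meant, because the exploratory section also uses log linear regression to obtain odds ratios for dichotomous outcomes. Neither reading matches the text.

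**2. Inputs.** The plan gives no expected value, zero share or power for endpoints 4–6, so there is no figure of its own to reproduce. From the power section: 408 children, 30% mild and 70% moderate to severe, so 0.30 × 408 ≈ 122 and 0.70 × 408 ≈ 286. Everything else is assumed.

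- Settings A–E: count = Bernoulli(p) × (1 + Poisson(m − 1)), with (p mild, p severe, m mild, m severe) = A (0.15, 0.30, 1.4, 1.4); B (0.30, 0.60, 1.4, 1.4); C (0.60, 0.849, 2.0, 2.83); D (0.80, 0.80, 2, 4); E (0.95, 0.95, 2, 4). The true mean ratio is 2.0.
- Settings F–G: negative binomial with variance μ + μ², means 0.5 vs 0.75 (F) and 2 vs 3 (G). The true mean ratio is 1.5.

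Zero shares, for example: A = 1 − (122 × 0.15 + 286 × 0.30)/408 = 1 − 104.1/408 = 74.5%; G = (122/3 + 286/4)/408 = 112.2/408 = 27.5%.

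**3. Why the constant matters.** In A and B the non-zero counts have the same distribution in both groups. Dropping zeros therefore gives exactly 1.00. With log(y + c), the log ratio is (p severe − p mild) × E[log((y + c)/c) | y > 0], where y = 1 + Poisson(0.4).

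- c = 1: 0.670 × log 2 + 0.268 × log 3 + 0.054 × log 4 + … = 0.846. Ratios: A exp(0.15 × 0.846) = 1.14; B exp(0.30 × 0.846) = 1.29.
- c = 0.1: 0.670 × log 11 + 0.268 × log 21 + 0.054 × log 31 + … = 2.637. Ratios: A exp(0.15 × 2.637) = 1.485; B exp(0.30 × 2.637) = 2.21.

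The ratio keeps growing as c shrinks, so no value of c is neutral.

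**4. Simulation.** 5000 replicates per setting, two-sided 0.05, unadjusted. Entries are ratio [rejection rate].

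| Setting (zeros) | Zeros dropped | log(y+1) | log(y+0.5) | log(y+0.1) | Poisson, robust SE |
|---|---|---|---|---|---|
| A (74.5%) | 1.00 [5%] | 1.14 [88%] | 1.21 [89%] | 1.48 [90%] | 2.04 [80%] |
| B (49.0%) | 1.00 [5%] | 1.29 [100%] | 1.47 [100%] | 2.21 [100%] | 2.03 [>99%] |
| C (22.5%) | 1.41 [≈100%] | 1.58 [≈100%] | 1.86 [≈100%] | 2.75 [≈100%] | 2.01 [≈100%] |
| D (20%) | 2.03 [100%] | 1.49 [100%] | 1.59 [100%] | 1.72 [94%] | 2.00 [100%] |
| E (5%) | 2.03 [100%] | 1.61 [100%] | 1.74 [100%] | 1.90 [100%] | 2.00 [100%] |
| F (60%) | 1.12 [23%] | 1.12 [58%] | 1.18 [56%] | 1.35 [52%] | 1.51 [64%] |
| G (27.5%) | 1.27 [65%] | 1.27 [81%] | 1.35 [79%] | 1.55 [71%] | 1.51 [89%] |

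Read across a row, not down a column: each row is one data-generating setting.

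**5. Window.** With follow-up held to 14 days, a call on day 11 leaves observable time at most 14/11 = 1.27-fold different between children. Chart review also supplies visits.

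**6. Gate.** Endpoints 1–3 are dichotomous and yield odds ratios. Endpoints 4–6 yield geometric mean ratios as written, and endpoint 7 yields a relative cost. The odds-ratio condition cannot be applied to endpoints 4–7.

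**The case against.** The strongest reply is that this concerns secondary outcomes which the plan says it will explore, that model assumptions will be checked, and that a pre-specified constant or a two-part model would also settle the zeros. The first part is right and limits the weight of the point. The assumption check supplies no rule for zeros and no fallback model. A fixed constant would remove the open choice, but the constant would still determine the size of the ratio. A two-part model is a legitimate alternative that answers two questions instead of one. Preferring a count model is partly a choice of what to estimate.

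Some stronger inferences are tempting and do not hold.

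- *That the count model is shown to be right because it returns 2.0 or 1.5.* Those mean ratios were built into the settings, so it matches by design. In A and B the effect was also placed wholly in the zeros.
- *That the ratio can move from 1.00 to 2.75.* Those values come from different settings; only the range within a row is meaningful.
- *That significance is safe whichever constant is used, or that the count model always has more power.* In A the constants reject more often than Poisson (88–90% vs 80%), and a repeat run found them disagreeing in 7–10% of datasets. In F and G Poisson rejects more often.
- *That dropping zeros always hurts.* In D and E, where the zero share is equal in both groups, it does not.
- *That follow-up differs 17/11 = 1.55-fold between children.* That requires counting events after day 14, against the 14-day follow-up in Section IV.
- *That an offset of log(days observed) repairs early calls.* It assumes events accrue evenly over time, which the documents do not support for absence in an acute illness.

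**Conclusion.** The concern holds, for secondary endpoints 4–6 and the exploratory absenteeism outcomes only. The stated measure is undefined when zeros occur, and it is mislabelled if a count model is intended. Within one setting, the log-scale ratio runs from 1.00 to 1.48 (A) or 1.00 to 2.21 (B) against a true mean ratio of 2.0, and from 1.12 to 1.35 (F) or 1.27 to 1.55 (G) against 1.5. Compared with Poisson regression with robust errors, dropping zeros lowers the rejection rate from 80% to 5% in A and from 89% to 65% in G. Added constants change significance less, and neither approach is always more powerful.

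These sizes rest on assumed counts and unadjusted models; the true zero shares are unknown. The mismatch in endpoint 4 and the inapplicable gate need no assumption, since both stand in the text. Nothing here touches the hospitalization analysis or the 408. It should be fixed before the data are analysed.

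**What to change.** - **Model.** In the Aim #2 text, and for absenteeism days under Exploratory Objectives #1-2, replace the log linear model and its geometric mean ratios with negative binomial regression on the untransformed counts. Name Poisson regression with robust standard errors as the fallback if it does not converge. Keep the same covariates and report mean ratios with 95% CI.
- **Denominator.** Restrict endpoint 5 to children who attend school or daycare and endpoint 6 to caregivers who work, so that not applicable is never entered as zero.
- **Window.** Apply the existing 14-day follow-up by asking at the call about the first 14 days only. Do not use a log(days observed) offset as the main analysis. For calls on days 11–13, take visits from the chart review and repeat the analysis without those children as a sensitivity check.
- **Endpoint 4.** Define it once as ED or healthcare-provider visits after the index visit, in line with Aim #2, Section IV.A and Section IV.C, and use that wording in Section IV.F.
- **Gate.** In the sensitivity-analysis paragraph, state the condition for endpoints 4–7 as a significant ratio above 1 on the scale each model reports: mean ratio for 4–6, cost ratio for 7.

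The cost is mostly SAP wording. The follow-up question must be limited to 14 days, and school or daycare attendance and caregiver employment must be recorded if the form does not already do so. The measure becomes a ratio of arithmetic means, which gives long absences more weight; the 14-day limit contains this.
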